Recently, authors have advocated for alternative methods of management of the predicted difficult airway, most commonly by using a video laryngoscope to perform the awake intubation. A video laryngoscope provides an indirect view of the larynx using a camera at the tip of a rigid laryngoscope. It takes less training to gain and maintain proficiency compared to flexible bronchoscopy.

Previous studies that have shown successful awake intubation with video laryngoscopy in the predicted difficult airway have not included patients with head and neck pathology, including malignancies or a history of head and neck surgery or radiation. Video

	Protocol Title:	Evaluation of Video Laryngoscopy in Patients with Head and Neck Pathology
	Principal Investigator Name/Contact Info:	[name] [contact]
	Primary Contact Name/Contact Info:	[name] [name]
	Date Revised:	3/13/2018
	Study Number:	GCO#17-0963/IF2253490

laryngoscopy may be more prone to failure in this patient population, and randomizing this population to video laryngoscopy would pose too great a risk.

If results of previous studies are erroneously generalized, anesthesiologists' skills in flexible bronchoscopy will decline. We therefore propose to perform video laryngoscopy in patients with head and neck pathology who require awake bronchoscopic intubation for surgery after placement of the tracheal tube and induction of anesthesia. This will allow us to approximate what the laryngeal view would have been with video laryngoscopy. If there is a significant incidence of difficult video laryngoscopy in this patient population, it will reinforce that anesthesiologists need to continue to learn and maintain skills in bronchoscopic intubation.

Objectives:

Research Question: In patients with predicted difficult airways due to head and neck pathology (malignancy or a history of surgery or radiation therapy) who undergo awake bronchoscopic intubation, what proportion would have been possible to intubate with video laryngoscopy?

Hypothesis: A significant proportion of patients with head and neck pathology will have poor laryngeal views with post-induction video laryngoscopy by experienced anesthesiologists.

Primary objective: Determine the incidence of difficult (Cormack-Lehane grade >2) video laryngoscopic view of the larynx after awake flexible bronchoscopic intubation in patients with head and neck pathology

Secondary objectives:

- a) grade the view (Cormack-Lehane) obtained by video laryngoscopy after awake flexible bronchoscopic intubation in patients with head and neck pathology
- b) grade the view (Cormack-Lehane) obtained by video laryngoscopy after awake flexible bronchoscopic intubation in patients with head and neck masses
- c) grade the view (Cormack-Lehane) obtained by video laryngoscopy after awake flexible bronchoscopic intubation in patients with a history of neck radiation

1) Background

	Protocol Title:	Evaluation of Video Laryngoscopy in Patients with Head and Neck Pathology
	Principal Investigator Name/Contact Info:	[name] [contact]
	Primary Contact Name/Contact Info:	[name] [name]
	Date Revised:	3/13/2018
	Study Number:	GCO#17-0963/IF2253490

Awake flexible bronchoscopic intubation is considered the gold standard in the management of the anticipated difficult airway.¹ More recently, this has been called into question,² with alternative intubation techniques described in both asleep and awake patients. In particular, many have advocated the use of awake video laryngoscopy.^{3,4} However, these studies did not include patients with head and neck pathology such as airway masses or previous neck radiation.

Advantages cited for videolaryngoscopy include faster intubation time, less training required to gain and maintain skills, creation of space within the airway to suction secretions, view of the tracheal tube during intubation of the larynx (as opposed to blind “railroading” of the tube over the bronchoscope), lower cost, and easier maintenance of equipment. Disadvantages of videolaryngoscopy include possible increased risk of failure due to gag reflex unable to be attenuated with topical anesthesia, inability to use with very limited mouth opening, and inability to move around fixed lesions. While video laryngoscopy has a well-established role in management of the difficult airway, it does have recognized limitations and failures. There appears to be an increased risk of failure of video laryngoscopy in patients with airway masses, neck pathology, and neck radiation⁵ plausibly because a flexible scope would be required to move around immobile tissues. Neither direct nor indirect video laryngoscopy can accomplish this necessary flexibility. Randomizing this patient population, for whom awake flexible bronchoscopic intubation is the gold standard, to other techniques would be unsafe, as multiple laryngoscopies can increase the difficulty of airway management. As these patients have been excluded from previous randomized studies, the results of these studies cannot be generalized to the head and neck pathology patient population. This study aims to assess the utility of video laryngoscopy in this patient population by performing a video laryngoscopy after the endotracheal tube is safely secured by awake bronchoscopy to get an estimate of what the laryngeal view would have been had awake video laryngoscopy been used for the intubation. While laryngoscopy conditions are not identical after an endotracheal tube is already in place and the patient is anesthetized, it is the most appropriate study design to ensure safety in this patient population.

If we find a significant number of difficult video laryngoscopies in this patient population, it will reinforce the need for anesthesiologists to maintain skills in flexible bronchoscopic intubation. Despite clear clinical indication and a good safety and success profile, experienced anesthesiologists may incorrectly forego awake bronchoscopic intubation. Qualitative analysis of cases in the United Kingdom’s Royal College of Anaesthetists’ 4th National Audit Project (NAP4) revealed elements of poor airway management in >75% of reports. Upper airway malignancy or disease processes of the head and neck were present in 40% of cases presented to NAP4. The report found

	Protocol Title:	Evaluation of Video Laryngoscopy in Patients with Head and Neck Pathology
	Principal Investigator Name/Contact Info:	[name] [contact]
	Primary Contact Name/Contact Info:	[name] [name]
	Date Revised:	3/13/2018
	Study Number:	GCO#17-0963/IF2253490

numerous cases where awake intubation was indicated but not used, possibly due to poor judgment, lack of skills, or lack of equipment.⁶

Bronchoscopy skills are challenging to attain and are prone to decay, potentially leading to practitioner discomfort with awake flexible bronchoscopy if not continually practiced.^{7,8} This study aims to add to the current body of knowledge regarding the use of video laryngoscopy for the predicted difficult airway, specifically in the head and neck pathology patient population. Unlike previous publications, this study will provide a safe way to evaluate the use of video laryngoscopy in patients with head and neck malignancy and/ or previous head and neck surgery or radiation. Information from this study will help guide future strategies in difficult airway management. Our hypothesis is that the anatomy in this patient population does not lend itself to straightforward video laryngoscopy, and that flexible bronchoscopy continues to have a vital role in the management of these airways.

2) **Setting of the Human Research**

This study will be conducted at the Icahn School of Medicine at Mount Sinai at [name] in the 7th floor Annenberg Building operating rooms. Consent will be obtained in the preoperative holding area, and the study protocol will occur in the operating room in which the patient is assigned.

3) **Resources Available to Conduct the Human Research**

100 participants will be enrolled in this study. Between 3-10 awake intubations with a flexible bronchoscope are performed per week in patients with head and neck pathology coming to the Annenberg 7 operating rooms. Assuming conservatively that we can enroll 1-2 patients per week, we anticipate completing the study within two years after initiation.

Drs. [name], [name], and [name] are attending anesthesiologists with substantial experience in supervising and performing awake flexible bronchoscopic intubations and post-induction video laryngoscope intubations. We also each have previous experience with research involving ENT surgical patients in the same practice setting, and well-established professional relationships with our ENT surgical and nursing colleagues to help support the study.

Prior to initiating this study, all participating investigators and support staff will conduct a protocol initiation meeting to ensure adequate

	Protocol Title:	Evaluation of Video Laryngoscopy in Patients with Head and Neck Pathology
	Principal Investigator Name/Contact Info:	[name] [contact]
	Primary Contact Name/Contact Info:	[name] [name]
	Date Revised:	3/13/2018
	Study Number:	GCO#17-0963/IF2253490

knowledge of the study objectives, procedures, populations, and human subject protections. A log of meeting attendees will be maintained.

4) Study Design

a) Recruitment Methods

Patients who are determined to require an awake flexible bronchoscopic intubation by the anesthesiologist caring for the patient on the day of surgery will be invited to participate in the study. After preoperative evaluation and explanation of the anesthetic plan and the awake flexible bronchoscopic intubation, the study will be explained in detail to the patient. All questions will be answered and if the patient agrees to participate, written informed consent will be obtained prior to entry into the operating room.

b) Inclusion and Exclusion Criteria

Inclusion criteria:

1. Age \geq 18 years
2. Presence of oral, pharyngeal or laryngeal mass or history of surgery or radiation for head and neck cancer
3. Requiring awake flexible bronchoscopic intubation for surgery
4. Willing and able to provide informed consent

Exclusion criteria:

1. Emergency procedure
2. Presence of one or more loose teeth

c) Number of Subjects

100 subjects will be included in this study.

d) Study Timelines

Patients will be screened and consented on the day of surgery. The awake bronchoscopic intubation and asleep video laryngoscopy will be performed prior to the start of surgery. All patients will be seen in the hospital (or called at home postoperatively for ambulatory surgical patients) within 48 hours to assess for any delayed complications. As

	Protocol Title:	Evaluation of Video Laryngoscopy in Patients with Head and Neck Pathology
	Principal Investigator Name/Contact Info:	[name] [contact]
	Primary Contact Name/Contact Info:	[name] [contact]
	Date Revised:	3/13/2018
	Study Number:	GCO#17-0963/IF2253490

patients only need to be followed for a maximum of 48 hours after discharge to be assessed for all primary and secondary endpoints, we estimate the study will be complete within 2 weeks of final patient enrollment.

e) Study Endpoints

Primary objective: Determine the incidence of difficult (Cormack-Lehane grade >2) video laryngoscopic view of the larynx after awake flexible bronchoscopic intubation in patients with head and neck pathology.

Secondary objectives:

- a) grade the view (Cormack-Lehane) obtained by video laryngoscopy after awake flexible bronchoscopic intubation in patients with head and neck pathology
- b) grade the view (Cormack-Lehane) obtained by video laryngoscopy after awake flexible bronchoscopic intubation in patients with head and neck masses
- c) grade the view (Cormack-Lehane) obtained by video laryngoscopy after awake flexible bronchoscopic intubation in patients with a history of neck radiation

Subjects will be withdrawn from the study and video laryngoscopy will not be performed if the awake flexible bronchoscopy fails and the patient cannot be intubated, or if there is difficulty with the awake flexible bronchoscopy resulting in tissue trauma.

f) Procedures Involved in the Human Research

Patients who are undergoing non-emergency surgery who have a history of head and neck pathology (masses, previous surgery, and/or radiation) who as determined by the anesthesiologist caring for the patient must undergo awake flexible bronchoscopic intubation will be invited to participate in the study after preoperative evaluation prior to entry into the operating room. Once in the operating room, intravenous access will be obtained and American Society of Anesthesiologists' standard monitors (pulse oximeter, electrocardiogram tracing, blood pressure cuff) will be applied. The patient will receive glycopyrrolate 0.2mg-0.4mg and sedation as per the usual practice of the anesthesiologist. Airway topicalization with lidocaine and awake flexible bronchoscopic intubation will be performed. After the tracheal tube is secured and general anesthesia is

	Protocol Title:	Evaluation of Video Laryngoscopy in Patients with Head and Neck Pathology
	Principal Investigator Name/Contact Info:	[name] [contact]
	Primary Contact Name/Contact Info:	[name] [name]
	Date Revised:	3/13/2018
	Study Number:	GCO#17-0963/IF2253490

induced, the attending anesthesiologist will perform video laryngoscopy with the C-MAC D video laryngoscope and with the GlideScope AVL video laryngoscope and grade the view of the larynx obtained with each laryngoscope. Care will be taken to minimize tissue trauma and hemodynamic perturbations caused by video laryngoscopy. All patients will receive 10mg of intravenous dexamethasone to reduce airway edema.

All participants will be monitored by the anesthesia team throughout the surgical procedure and until handoff of care to the Post-Anesthesia Care Unit (PACU) nurse as per usual practice. All subjects will be evaluated for the appearance of any delayed complications within 48 hours of the end of the procedure. Relevant data will be collected from the patient, anesthesiologist, EPIC, and Compurecord.

All medications administered and procedures performed are identical to those performed if not enrolled in the study, with the only exception being the video laryngoscopy.

Data to be collected:

Age
Gender
Body Mass Index (BMI)
Mallampati score
Head and neck pathology: 
 a) Location of mass, if present b) History of surgical procedure c) History of radiation
Visual Analog Score (VAS) of ease of bronchoscopic intubation by anesthesiologist
C-MAC Video Laryngoscope Cormack-Lehane View (grade 1-4)
GlideScope AVL Video Laryngoscope Cormack-Lehane View (grade 1-4)

	Protocol Title:	Evaluation of Video Laryngoscopy in Patients with Head and Neck Pathology
	Principal Investigator Name/Contact Info:	[name] [contact]
	Primary Contact Name/Contact Info:	[name] [name]
	Date Revised:	3/13/2018
	Study Number:	GCO#17-0963/IF2253490

Occurrence of any complications

g) Specimen Banking

N/A

h) Data Management and Confidentiality

All researchers who will access the data have completed the institutional HIPAA certification. Extracted data will be de-identified before being given to the statistician for analysis. Any intermediary data files containing extracted PHI will be stored on secured hospital servers and destroyed after data analysis is complete. All study data at Mount Sinai stored electronically will follow MSMC policies. All PHI that is not stored on a limited access Mount Sinai IT maintained network drive will be encrypted and password protected. Statistical analysis will be carried out by a statistician employed by the Department of Anesthesiology. When the de-identified data set are released for analysis, a one-way hash ID will be generated for each record. Only Mount Sinai study investigators with access to the full data set will be able to match the hash ID to the original source

i) Provisions to Monitor the Data to Ensure the Safety of subjects

MSSM Principal Monitor (PI):

Last Name: [name]
 First Name: [name]
 Academic Title: Assistant Professor
 Department: Anesthesiology, Perioperative, and Pain Medicine
 Mailing Address: [name]
 [contact]
 E-mail: [contact]

MSSM Additional Monitor (Co-investigator):

Last Name: [name]
 First Name: [name]
 Academic Title: Associate Professor
 Department: Anesthesiology, Perioperative, and Pain Medicine
 Mailing Address: [name]
 [contact]
 E-mail: [contact]

	Protocol Title:	Evaluation of Video Laryngoscopy in Patients with Head and Neck Pathology
	Principal Investigator Name/Contact Info:	[name] [contact]
	Primary Contact Name/Contact Info:	[name] [name]
	Date Revised:	3/13/2018
	Study Number:	GCO#17-0963/IF2253490

[name] and [name] are board certified anesthesiologists with expertise in difficult airway management. All subjects will be monitored closely in the immediate perioperative period by the anesthesia team caring for the patient. Participants will also be seen postoperatively within 48 hours to assess for delayed complications, or called by telephone in the case of ambulatory procedures. Ambulatory participants will also receive instructions and a business card in order to have a point of contact to report a potential adverse event at any time during or after participation. They will also be specifically informed that they should receive emergency department care for any signs or symptoms of airway compromise. Any serious adverse event will be recorded by the research team in a non-anonymized fashion and reported directly to the Mount Sinai Institutional Review Board.

j) Withdrawal of Subjects

Subjects will be immediately withdrawn from the study if:

- Any difficulty resulting in airway injury occurs during the initial awake bronchoscopic intubation
- The awake bronchoscopic intubation is not able to be performed successfully

If withdrawn from the study, the anesthesiologist will not perform the planned laryngoscopy with the video laryngoscope.

5) Risks to Subjects

It is reasonably foreseeable that participants will have an increased risk of sore throat from the addition of video laryngoscopy.

Video laryngoscopy has the potential cause damage to oropharyngeal structures, including but not limited to: dentition, hard palate, soft palate, epiglottis, vocal cords, larynx, and soft tissue. These injuries are more likely to occur when struggling to obtain an adequate view of the larynx in order to intubate, which will not be the case for this study. Since the airway will be protected with an endotracheal tube during laryngoscopy, damage/ bleeding in the airway should not lead to issues with oxygenation or ventilation.

There is a risk of hemodynamic changes during laryngoscopy. The anesthesiologist will have the ability to treat tachycardia, bradycardia, hypertension, and hypotension with the appropriate pharmacologic agents.

	Protocol Title:	Evaluation of Video Laryngoscopy in Patients with Head and Neck Pathology
	Principal Investigator Name/Contact Info:	[name] [contact]
	Primary Contact Name/Contact Info:	[name] [name]
	Date Revised:	3/13/2018
	Study Number:	GCO#17-0963/IF2253490

There is a slight risk of unintentional extubation during laryngoscopy- if this is to happen the anesthesiologist should be able to reintubate the patient using either the flexible bronchoscope or video laryngoscope, but it is possible that reintubation would be difficult.

There is a slight risk of having to keep the patient intubated postoperatively due to continued bleeding or swelling from damage during video laryngoscopy. If this is to occur, the patient will be admitted to an acute care setting for further ventilation management and eventual extubation.

6) **Provisions for Research Related Injury**

Subjects will be monitored during surgery and during recovery from anesthesia. Upon discharge, subjects will be provided with a phone number to call should they have any concerns related to surgery, anesthesia, or the study. If necessary, subjects will be instructed to return to the hospital should any complication requiring medical attention occur, or to the nearest emergency department for any signs of airway compromise.

Subjects who are injured as a result of this study will be treated until the resolution of the adverse event and the cost billed to them and/or their insurance carrier. Patients will not be compensated for research related injury, with the exception of damage to dentition that occurs during the course of anesthetic care, which is routinely covered by the department of anesthesiology.

Anesthesiologists and intensive care unit staff will be available to maintain ventilation and airway management in the event of airway damage/bleeding requiring prolonged intubation. ENT surgeons will be present in the operating room and immediately available in the unlikely case of need for an emergent surgical airway. ENT surgeons would also be available for evaluation and treatment of non-emergent oropharyngeal injuries.

7) **Potential Benefits to Subjects**

Participation in this study will not lead to any direct benefit to the patient.

8) **Provisions to Protect the Privacy Interests of Subjects**

The de-identified data will be stored on secure, password-protected servers maintained by Mount Sinai Information Technology (IT). Access to the data will only be available to Mount Sinai IT administrators, the primary investigator, and co-investigators. When the de-identified data set are

	Protocol Title:	Evaluation of Video Laryngoscopy in Patients with Head and Neck Pathology
	Principal Investigator Name/Contact Info:	[name] [contact]
	Primary Contact Name/Contact Info:	[name] [name]
	Date Revised:	3/13/2018
	Study Number:	GCO#17-0963/IF2253490

released for analysis, a one-way hash ID will be generated for each record. Only study investigators with access to the full data set will be able to match the hash ID to the original record. All investigators have completed HIPAA training regarding maintaining patient PHI confidentiality.

During the preoperative evaluation, subjects will be asked what number they prefer to be contacted at after discharge. They will also be asked whether it is ok for an investigator to leave a message. All messages will be of a general nature and will not contain personal health information. Moreover, post-operative evaluation by phone within the 48 hours following surgery is routine practice.

9) Economic Impact on Subjects

There are no costs to subjects for participating in this study. There will be no additional visits or tests related to study participation

10) Payment to Subjects

There is no payment to subjects

11) Consent Process

Eligible patients will be invited to participate in the study by an investigator after the preoperative evaluation in the preoperative holding area on Annenberg 7 on the day of surgery. A study investigator will describe the study in detail, answer questions, confirm understanding, and provide the consent form for review. The patient will be given privacy to review the consent form in detail and will then have another opportunity to ask questions prior to signing consent. The voluntary nature of this study will be emphasized, and patients who initially agreed to participate may choose to decline participation any time prior to anesthetic induction. Participants will be asked about the study to confirm understanding prior to providing written informed consent. Non-English speaking subjects will not be eligible for this study. SOP HRP-090 will be followed.

12) Process to Document Consent in Writing

Consent will be documented using the standard PPHS consent template

13) Vulnerable Populations

No vulnerable populations will be included in this study

14) Multi-Site Human Research (Coordinating Center)

	Protocol Title:	Evaluation of Video Laryngoscopy in Patients with Head and Neck Pathology
	Principal Investigator Name/Contact Info:	[name] [contact]
	Primary Contact Name/Contact Info:	[name] [name]
	Date Revised:	3/13/2018

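### Is the primary incidence left undefined because each patient is graded with two video laryngoscopes?

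*Combined protocol and SAP*

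**What the plan says.** The primary objective is worded alike under Objectives and in section 4e: "Determine the incidence of difficult (Cormack-Lehane grade >2) video laryngoscopic view of the larynx after awake flexible bronchoscopic intubation". It is a single incidence with no device attached. The secondary objectives are also written in the singular, for example "grade the view (Cormack-Lehane) obtained by video laryngoscopy after awake flexible bronchoscopic intubation in patients with head and neck masses".

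Section 4f has the attending perform video laryngoscopy twice after induction, first with the C-MAC D and then "with the GlideScope AVL video laryngoscope and grade the view of the larynx obtained with each laryngoscope". The list of data to be collected has two separate items, "C-MAC Video Laryngoscope Cormack-Lehane View (grade 1-4") and "GlideScope AVL Video Laryngoscope Cormack-Lehane View (grade 1-4"). It has no item for a best, worst or combined view.

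The research question asks "what proportion would have been possible to intubate with video laryngoscopy". The Background describes the aim as "an estimate of what the laryngeal view would have been had awake video laryngoscopy been used for the intubation". Neither names a device. On analysis, section 4h says only that a departmental statistician will do it. Section 4c sets 100 subjects; sections 4e and 4j provide that withdrawn patients have no video laryngoscopy, so the two grades exist for examined patients only.

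**The concern.** The endpoint is one number and the data give two grades per patient. When the devices disagree about a patient, the written objective does not say whether that patient counts as difficult. Three definitions fit the text: the incidence with one named device, the incidence with each device, or the proportion difficult with both (nobody could obtain a good view with either instrument). Two careful analysts could report different headline figures from the same data.

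This is the only primary result, and the hypothesis is directional: the investigators expect many poor views. With no numerical threshold, the estimate carries the conclusion. If the definition were settled only after the grades were seen, it could be settled in the direction the investigators expect.

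**Working it through.** **What the text supports.** Set side by side, the passages do not weigh equally.

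- Section 4f and the data list grade and record each device separately, with no composite. They point to one incidence per device, and likewise to one grade distribution per device for secondary objectives a to c.
- The research question can be read as favouring a both-device rule, since a patient with a good view on either device might have been intubated. It does not say so.
- The stated aim of estimating the view under awake video laryngoscopy is neutral between devices.
- No passage suggests counting a patient as difficult when either device alone gives a poor view.

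Per-device reporting is therefore the natural default, although it is not stated.

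**What the default preserves.** Let a = difficult with both devices, b = with the C-MAC only, c = with the GlideScope only, d = with neither. Then:

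- C-MAC incidence = (a + b)/N
- GlideScope incidence = (a + c)/N
- both-device incidence = a/N

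The two recorded grades give all four counts, so no definition is lost by the way the data are collected.

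**How far the definitions could differ.** The plan gives no expected rate, precision target or between-device agreement, so there is no planned figure to reproduce and every input except N = 100 is an assumption. Take an equal rate p on each device and a correlation phi between the two difficult/not-difficult outcomes:

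- both = p² + phi × p(1 − p)
- single − both = p(1 − p)(1 − phi)
- proportion discordant = 2p(1 − p)(1 − phi)

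At p = 0.30, p(1 − p) = 0.21. At phi = 0.5, for example, both = 0.09 + 0.105 = 19.5%, and single − both = 0.21 × 0.5 = 10.5 points.

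| phi | Both devices | Single − both, p = 30% | p = 10% | p = 50% |
|---|---|---|---|---|
| 0.3 | 15.3% | 14.7 | 6.3 | 17.5 |
| 0.5 | 19.5% | 10.5 | 4.5 | 12.5 |
| 0.7 | 23.7% | 6.3 | 2.7 | 7.5 |
| 0.9 | 27.9% | 2.1 | 0.9 | 2.5 |

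(Differences in percentage points. The both-devices column is for p = 30%.)

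For scale, the exact 95% interval for 30/100 is 21.2% to 40.0%, so its lower arm is 8.8 points. Single − both equals that arm at phi = 1 − 0.0876/0.21 = 0.58. Below that agreement the choice of definition moves the figure by more than the lower arm; above it, by less.

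**Choosing the device after the fact.** With equal true rates, the expected excess of the higher of two observed incidences is about 0.5 × √(2/π) × √(discordant/N). At p = 0.30, N = 100 and phi = 0.3, discordant = 0.294 and the excess is 0.5 × 0.798 × √0.00294 = 0.0216, or 2.2 points. At phi = 0.5, 0.7 and 0.9 it is 1.8, 1.4 and 0.8 points.

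**Direction.** A both-device incidence can never exceed either single-device incidence. Moving from the default to a both-device rule therefore works against the hypothesis.

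**The case for a change.** The strongest argument for a change is that this is the sole primary number, that a definition costs a few sentences, and that agreement will be unknown until the data are in, when a choice can no longer be independent of them. At low to moderate agreement the single-device and both-device figures differ by more than the sampling error on one side of the estimate. It is true that the plan does not state the definition, and a sentence confirming per-device reporting would be harmless.

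The rest is weaker:

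- The Background remark that "multiple laryngoscopies can increase the difficulty of airway management" might be taken to favour a single-device estimate. In context it explains why randomising these patients would be unsafe, and it has no bearing on how to count a patient graded twice.
- If true rates differed, say 25% and 35%, the choice of device would move the result by 10 points. That figure only restates the assumed difference, and it argues for showing both devices, which is the default.
- The widest contrasts come from counting a patient as difficult with either device, a rule the documents nowhere suggest.
- The text does not require an early choice, but neither does it force a late one.

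**Conclusion.** No change to the plan is needed. The definition is unstated, but the way the data are collected points to a sensible one: an incidence of grade above 2 for each device, among examined patients. No written rule produces a wrong result, both grades are kept, and the study is descriptive, with no test or success threshold that turns on the choice. A report giving both device incidences and the paired table would expose any selective choice and let a reader compute the both-device figure.

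Under the assumptions above (equal rates of 30%, correlation 0.3 to 0.9), the definitions differ by 14.7 down to 2.1 points, and after-the-fact choice of device by 2.2 down to 0.8 points at N = 100. The documents supply neither the rates nor the agreement, so these figures bound what could happen and do not show that the effect is large here. The same attending grades both views, which makes high agreement, and so a small effect, possible. This conclusion covers the text available for this review. It would be weaker if the results were reported for one device only, or as a combined figure alone.
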